4.2.6 Summary Measure of the Estimand

Percent (and 95% CI) of subjects achieving EASI-75 at Week 14 in the lirentelimab SC and Placebo treatment groups and the absolute difference (and 95% CI) in the percent response between treatments.

5. Statistical Methods

5.1 General Methodology

All statistical analyses will be conducted using SAS v9.4 or later version on the Microsoft Windows Operating System.

All eCRF data (raw data) will be converted into SDTM (Study Data Tabulation Model) datasets, which will be used to create ADaM (Analysis Data Model) data sets. The creation of the SDTM and ADaM data sets will follow the CDISC (Clinical Data Interchange Standards Consortium) standards and the FDA Study Data Technical Conformance Guide. All analysis tables and listings will be created from the ADaM data sets.

Continuous data will be summarized using "n" (number of subjects with non-missing observations), mean, median, standard deviation (SD), minimum value, and maximum value. Categorical data will be summarized using the frequency count and percentage (n, %) of subjects in each category. Number of subjects with non-missing values or number of subjects with missing values (e.g., Not Done) will be presented, where appropriate. Subjects with missing values will not contribute to the denominator for percentage calculations, unless specified otherwise. Counts of 0 in any category will be presented without percentage. All summaries will be presented for individual treatment groups. In addition, for summary of disposition and subject baseline characteristics, the presentation will include both treatment groups combined.

The precision rules for the presentation of summary statistics will be:

- Sample size (n, N) and number of missing responses (if displayed): Integer
- Mean, confidence interval, and median: Same number of decimal places as reported/collected
- Standard deviation: Same number of decimal places as reported/collected
- Percentiles, minimum, maximum: Same number of decimal places as reported/collected
- Odds Ratio: 2 decimal places

- Percentage: 1 decimal place generally, or 2 decimal places for <0.1%, or no decimal places for 0% and ≥100%
- P-value: 4 decimal places
- WBC: 2 decimal places as $0.01 \times 10^9/L$
- Height/Weight/BMI: 1 decimal place

The data summaries will be accompanied by individual subject data listings. All data available from questionnaires, eCRF, and external transfer (labs) will be listed and will include relevant subject information, e.g., treatment group and study day. The listings will be sorted in the order of treatment group, subject ID, assessment name and date/time.

Dates will be presented in the ISO-8601 format YYYY-MM-DD. Times will be displayed in 24-hour clock format. Numbering for tables, figures and listings will follow ICH E3 Guideline (ICH, 1996).

Alternative methods of analysis of the data may be considered prior to database lock, and reason for departure from the planned methods will be documented in an amendment to the SAP or in the CSR.

5.2 Visit Window and Unscheduled Assessments

Data collected for study assessments provide information on the status of the subject at a given time point. Assessments will be slotted into analysis windows to allow summaries to be performed for subjects with similar study drug exposure. The analysis windows are described in Table 1 by the target study days (see Table 2) of the planned visits. For example, for visit description Day 8, the window is ± 3 days of the visit description.

In the event of multiple values from unscheduled or early termination assessments within a single analysis window, the value closest to the scheduled visit target study day will be used for analyses. If 2 values tie as closest to the time point (for example, 1 value is before and the other value is after the time point), then the later value will be selected. Data collected at all visits will be included in the data listings with visit presented as reported by the site.

eDiary daily results (ppNRS) will be summarized by Study Week as outlined in Table 2.

5.3 Adjustment for Covariates

Efficacy analyses will be adjusted for baseline values and randomization strata using ANCOVA, MMRM, or Cochran-Mantel-Haenszel tests, where applicable.

5.4 Data Handling Conventions

This section includes the methods for missing data imputation for some summary analyses, if necessary.

Adverse events with incomplete start or stop dates (i.e., either day or month is missing) will be considered treatment-emergent adverse events (TEAE) unless the partial start date or the stop date confirms the AE started or ended prior to Study Day 1 (e.g., the day of the AE start date is unknown but the month and year indicate that the AE starts prior to Study Day 1). Adverse events with missing relationship to study drug will be included in the "Related" category for the summary tables and footnoted. Adverse events with missing severity will not be included in the by-severity summary table but will be footnoted in the table.

When there is incomplete information regarding dosing dates for prior and concomitant medication, the medication will be considered as a concomitant medication unless it contradicts with the stop date. For example, a medication will be considered a prior medication if the month and year of the end date indicates a date before Study Day 1 even though the start date could be missing.

5.5 Independent Safety Monitoring and Interim Data Analysis

An independent Data Monitoring Committee (iDMC) has been convened for this study. The iDMC will meet at established intervals (as per the iDMC charter) throughout the study and will also convene as necessitated by data and/or safety reviews.

No interim analysis will be conducted for this study.

5.6 Timing of Data Analyses

The database lock will occur after all subject's complete participation in the double-blind period of the study.

For the database lock, applicable EDC data will be locked to protect write access after the following preconditions are fulfilled:

- All records are entered in the database.
- All AE are coded to the satisfaction of the Chief Medical Officer.

- All medications are coded to the satisfaction of the Chief Medical Officer.
- All data queries have been resolved.
- All decisions have been made regarding all protocol violations and ITT population exclusions.
- Written authorizations to lock the database are obtained from Allakos Clinical Data Management and the Chief Medical Officer.

The randomization code for this study will not be revealed until the previous preconditions are fulfilled, and documentation of the database lock is complete. After the database lock, the randomization code will be made available to individuals at Allakos who are involved in the data analysis. Data analysis will commence after the data lock. In addition, the PK and ADA data may be locked and assessed separately.

5.7 Multicenter Study

The study will have approximately 70 sites in the US and Germany. For efficacy analysis, sites within countries will be pooled together.

5.8 Multiple Comparisons/Multiplicity Adjustment

To control for the family-wise type-I error rate, the following testing procedures will be implemented:

Test primary efficacy endpoint at 2-sided α =0.05 level.

- If p≤0.05 for primary endpoint, then reject the null hypothesis that lirentelimab SC is no different from placebo and accept the alternative hypothesis that lirentelimab SC is superior to placebo in improving EASI score.
- If p≤0.05 for primary endpoint, the hypothesis tests for the secondary endpoints will
 proceed in the prespecified order (see Section 2.2). If at any point during the analysis of the
 secondary endpoints, the statistical test is not significant at 2-sided α=0.05 level, the
 hypothesis testing procedure will stop. Lirentelimab SC will be deemed superior to placebo
 for all endpoints prior to the stop.

5.9 Examination of Subgroups

Key endpoints will be summarized by subgroup to assess the consistency of the treatment effect across each of these subgroups. For any subgroup, if there are zero subjects within a stratification stratum in any treatment group, the statistical model will not be adjusted by the stratification factors. Subgroups to be considered are:

- Sex (Male, Female)
- Age group ($<65, \geq 65$)
- Race (White, Non-White)
- Age of disease onset (<18 years, \geq 18 years)
- Baseline disease severity index [moderate (IGA=3) and severe (IGA=4)]
- Baseline EASI severity index [moderate (EASI score ≤ 22) and severe (EASI score ≥ 22)]
- Body Surface Area (BSA) ($\geq 10\%$ <16%, $\geq 16\%$ -<40%, $\geq 40\%$)
- Prior biologics experience for the treatment of atopic dermatitis (biologic-naïve and biologic-exposed)

6. Statistical Analysis

6.1 Analysis Populations

The population of "all screened subjects" comprises subjects who signed the informed consent (ICF).

6.1.1 Safety Population

The safety population comprises randomized subjects who have received at least 1 dose of the study drug.

6.1.2 Intent-to-Treat Population

The intent-to-treat (ITT) population is defined as subjects who were randomized to treatment.

6.1.3 Modified Intent-to-Treat Population

The modified intent-to-treat (mITT) population will be defined as all randomized subjects who received at least one SC injection of study drug and had no major protocol violations based on key inclusion and exclusion criteria defining the population of interest (i.e., defined as not meeting any of the key inclusion criteria number 3, 4, 6, 7, 8 or meeting exclusion criteria number 8 in this study).

To assess the impact of excluding subjects from the efficacy analyses, results including all subjects (this population will be referred to as All Subjects All Data) and excluding the subjects who had any major protocol violation based on key inclusion and exclusion criteria defining the population of interest will be presented. The differences between these results will be noted, and the impact of such differences will be discussed in the clinical study report.

6.1.4 Per Protocol Population

The per protocol (PP) population will include the subjects in the mITT population who do not have any major protocol deviations or violations and who receive all 7 injections of study drug (see Section 6.3 for list of protocol deviations and violations).

6.2 Disposition of Subjects

Subject demographics and reasons for screening failure will be summarized for screen-failed subjects. Subjects (n and %) who completed or discontinued from the study will be tabulated by treatment group and for both treatment groups combined. The primary reasons for study discontinuation will be included in the tabulation. The primary reasons may include, but are not limited to, any of the following:

- Subject withdrew consent
- Lost to follow-up
- Administrative reason
- Adverse event
- Investigator decision
- Failure to follow required study procedures
- Other

Subject disposition will be summarized for the ITT population. Subject counts for the Safety, mITT, and PP populations will be included in the table. A data listing for subject disposition will be presented for the ITT population.

6.3 **Protocol Deviations and Violations**

Protocol deviations will include, but are not limited to

- Non-compliance with scheduled study visit
- Non-compliance with study treatment
- Received prohibited medications (see Protocol Section 8.5)
- Any major violations of efficacy-related entry inclusion or exclusion criteria (defined as not meeting inclusion criteria number 3, 4, 6, 7, 8 or meeting exclusion criteria number 8)
- Non-compliance with study assessment procedures

Subjects with major protocol deviations will be listed. The listing will include a brief description of the deviation, deviation category, and if applicable, study day when deviation occurred along

with other pertinent information. If warranted by the sample size, subjects (n and %) with major protocol deviations will be tabulated by treatment group and by deviation category.

Subjects who are excluded from the mITT and PP population will be listed with reasons for exclusion.

6.4 Demographics and Baseline Disease Characteristics

The following demographic and baseline characteristics variables will be summarized:

- Demographic variables: Age at screening (year), age group, sex, ethnicity, race, baseline weight (kg) with grouping (<60 kg, ≥60 kg), BMI (kg/m2) with grouping (<20, ≥20)
- Baseline characteristics: Age of disease onset with grouping (<18 years, ≥18 years), peak pruritus numerical rating scale (ppNRS), Investigator's Global Assessment (IGA) score, Eczema Area and Severity Index (EASI) score, SCORing Atopic Dermatitis (SCORAD) score, Body Surface Area (BSA) affected by AD, Dermatology Life Quality Index (DLQI)

Descriptive statistics for these variables will be presented for all populations, by treatment group, and both treatment groups combined. Continuous variables will be summarized with n, mean, SD, and median. Categorical variables will be summarized with n and % of subjects for each category for the mITT, and PP populations.

6.5 Medical History

Subject incidence (n and %) of medical history (and current medical condition before signing the informed consent) will be tabulated by the Medical Dictionary for Regulatory Activities (MedDRA), version 21.0) System Organ Class (SOC) and Preferred Term (PT).

6.6 Electrocardiogram

A listing of electrocardiograms (ECG) overall interpretation at screening visit will be provided.

6.7 Pregnancy Test

A listing of pregnancy test results will be provided.

6.8 Treatments

6.8.1 Treatment Compliance

Summaries of treatment compliance will be based on the safety population.

The compliance with study treatment will be calculated as follows:

Treatment Compliance = (Number of study drug injections during exposure period)/ (Number of planned study drug injections during exposure period) x 100%.

The treatment compliance will be presented by the following specific ranges for each treatment group: <80%, and $\ge80\%$.

In addition, an overall compliance that includes adherence to treatment administration schedule and any interruptions will be included in the data listing.

6.8.2 Prior, Concomitant, and Newly Initiated Medications

Prior medications and concomitant medications will be extracted from the Prior/Concomitant Medication CRF. Medications taken prior to Study Day 1 will be considered as prior medications, medications taken on or after Study Day 1 will be considered as concomitant medications, and newly initiated medication refers to any medication with a start date ≥ Study Day 1. We note that a Prior Medication may also be a Concomitant Medication if the start date is prior to Study Day 1 and the end date is on/after Study Day 1. Medications will be coded using the WHO Drug Dictionary (WHODD March 2018 release) for preferred term (PT) and Anatomical Therapeutic Chemical (ATC) classification.

Medications will be tabulated separately based on the Safety population. The number (n and %) of subjects taking at least 1 medication and the number (%) of subjects taking each medication at the preferred term level will be tabulated by ATC4, and PT. Subjects taking the same PT medication twice will only be counted once.

A subject data listing will be provided to include the reported medication name, the WHODD PT, ATC4, study day and pertinent subject information.

6.9 Analyses of Efficacy Endpoints

For all efficacy variables, the analysis will be comparison of lirentelimab SC and the placebo treatment groups. The following null and alternative hypotheses for the primary endpoint will be tested for lirentelimab SC group and the placebo group:

H₀: No treatment difference between lirentelimab SC and placebo

H₁: There is a treatment difference between lirentelimab SC and placebo

Baseline disease severity index [moderate (IGA=3) and severe (IGA=4)] and prior biologic experience (biologic-naïve and biologic-exposed) will be the 2 stratification factors for subject randomization and will be accounted for in the statistical modeling for efficacy. In addition, if it

is evident that the primary endpoint is confounded by study entry characteristics [e.g., the method of IGA and/or EASI score assessment by AD specialist (defined as the PI and or Sub-I being either an allergist, immunologist or dermatologist) as compared to non-AD specialist, change in percent BSA greater than 20% at the end of the Lead-in Phase (Day -14 to Day -8) compared to the end of the Baseline Phase (Day -7 to Day -1)], then the primary efficacy analysis will be conducted adjusting for the effects of the background characteristics.

6.9.1 Analysis of Primary Efficacy Endpoint

The primary responder endpoint will be analyzed using the Cochran-Mantel-Haenszel test adjusted by baseline disease severity index [moderate (IGA=3) and severe (IGA=4)], prior biologic experience (biologic-naïve and biologic-exposed), and country (USA and Germany) at Week 14. A sample SAS code is as follows:

```
* COMPUTES CMH P-VALUE AND NEWCOMBE COMMON RISK DIFFERENCE ;
ods output CMH=PVAL(where=(althypothesis='Row Mean Scores Differ'))
CommonPdiff=DIFF;
proc freq data=ADEF ;
      tables DISEASE_INDEX*BIOLOGIC_EXPERIENCE*COUNTRY*TRTP*RESP /
cmh(MF) commonriskdiff
(cl=NEWCOMBE) ;
run ;
```

The Mantel-Fleiss (MF) criterion will be performed, and if it is not met while using the option CMH (MF) in SAS procedure PROC FREQ, analyses including each factor separately in CMH test will be conducted. Should assumption per the MF criterion not be satisfied, the comparison will be based on a Fisher's exact test after collapsing across levels of the stratification factor and country.

Below is an example of the SAS code for the Fisher's exact test:

```
* COMPUTE 95% EXACT CONFIDENCE INTERVAL FOR %RESPONSE FOR INDIVIDUAL
TREATMENT ;
ods output BinomialCLs=CL ;
proc freq data=ADEF ;
    table RESP / out=CNTS bin(cl=midp) ;
    by TRTP ;
run;
```

For the analysis described above, subjects who prematurely discontinue the randomized treatment or initiate any treatment adjustments (e.g., use of prohibited/rescue medication/rescue treatment for AD symptoms) will be handled as described below:

- If a subject withdraws from the study, this subject will be counted as a non-responder for the time points after withdrawal
- To account for the impact of prohibited/rescue medication/rescue treatment for AD symptoms on the efficacy effect: if rescue medication/rescue treatment for AD symptoms is used (see Appendix 1: Intercurrent Events and Definitions of Prohibited Medication Use and Rescue Medication/Treatment for AD Symptoms for definitions of ICE and listings of prohibited medications and rescue medications/therapies), the subject will be specified as a non-responder from the time the rescue medication/rescue treatment is used
- If the subject has the missing value at Week 14, it will be counted as a non-responder at Week 14

The primary efficacy analysis will be performed on the mITT population, as well as PP population as a supporting analysis. In addition, for completeness purposes, results including all subjects and excluding the subjects who had major protocol deviations on the basis of key inclusion and exclusion criteria defining the population of interest will be presented. The differences between these results will be noted, and the impact of such differences will be discussed in the clinical study report.

6.9.2 Analysis of Secondary Efficacy Endpoints

The binary secondary efficacy endpoint will be analyzed using the same approaches as that are used for the analysis of the primary endpoint.

Mixed Model for Repeated Measures (MMRM) analyses will be performed on continuous endpoints to mitigate the impact of missing data. This approach assumes missing observations are missing at random and borrows information from subjects in the same treatment group, taking into account the missingness of data through the correlation of the repeated measurements.

All continuous endpoints will utilize MMRM after applying the primary censoring rule, i.e., the rule will censor data after permanent study drug discontinuation or after rescue therapy. This censoring rule is equivalent to using all the data up to discontinuation or rescue.

The MMRM model will include fixed effects for baseline value, disease severity group, biologicnaïve vs biologic-exposed, country, treatment, study week, the treatment-by-week interaction, and the baseline-by-week interaction and allow for random subject effects. Treatment and week will each be fitted as categorical variables. The model will assume unstructured covariance structure. If the model with unstructured covariance does not converge, then other covariance structures will be considered to model the within-subject errors. The Kenward-Rogers approach for computing denominator degrees of freedom will be used to account appropriately for pooling of within-subject and between-subject variance estimates. Efficacy data on subjects who prematurely discontinue the randomized treatment or initiate any treatment adjustments (e.g., use of prohibited/rescue medication/rescue treatment for AD symptoms) will be set to missing at the designated time points after withdrawal or after the start of such treatment changes. The LSM and 95% CI for the difference between groups will be estimated using the simple contrast at each time point. Below is an example of the SAS code for the MMRM:

```
proc mixed data=EASI method=reml;
    class TRTP USUBJID AVISITN COUNTRY DISEASE_INDEX
BIOLOGIC_EXPERIENCE;
    model PCHG= B_EASI TRTP AVISITN COUNTRY DISEASE_INDEX
BIOLOGIC_EXPERIENCE TRTP*AVISITN B_EASI*AVISITN / DDFM=KR;
REPEATED AVISITN / SUBJECT=USUBJID (TRTP) TYPE=UN;
RANDOM COUNTRY;
LSMEANS TRTP*AVISITN / PDIFF CL;
RUN;
```

Where TRTP = planned treatment group in numeric (1 = placebo, 2 = lirentelimab SC); AVISITN = time point (i.e., Weeks 2, 4, 6, 8, 10, 12, and 14).

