16.6.2 Secondary Efficacy Endpoint Analysis

The binary secondary efficacy endpoint will be analyzed using the same approaches as that are used for the analysis of the primary endpoint.

Mixed Model for Repeated Measures (MMRM) analyses will be performed on continuous endpoints to mitigate the impact of missing data. This approach assumes missing observations are missing at random and borrows information from subjects in the same treatment group taking into account the missingness of data through the correlation of the repeated measurements.

All continuous endpoints will utilize MMRM after applying the primary censoring rule, i.e., the rule will censor data after permanent study drug discontinuation or after rescue therapy. This censoring rule is equivalent to using all the data up to discontinuation or rescue.

The MMRM model will include fixed effects for baseline value, disease severity group, biologic-naïve vs biologic-exposed, country, treatment, study week, the treatment-by-week interaction, and the baseline-by-week interaction and allow for random subject effects. Treatment and week will each be fitted as categorical variables. The model will assume unstructured covariance structure. If the model with unstructured covariance does not converge, then other covariance structures will be considered to model the within-subject errors. The Kenward-Rogers approach for computing denominator degrees of freedom will be used to account appropriately for pooling of within-subject and between-subject variance estimates. Efficacy data on subjects who

prematurely discontinue the randomized treatment or initiate any treatment adjustments (e.g., use of prohibited/rescue medication/rescue treatment for AD symptoms) will be set to missing at the designated time points after withdrawal or after the start of such treatment changes. The LSM and 95% CI for the difference between groups will be estimated using the simple contrast at each time point.

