6.10 Analysis of Exploratory Endpoints

6.10.1 Change from Baseline in

The endpoint will be analyzed using the same approaches as that are used for the analysis of the secondary efficacy continuous endpoint of percent change in EASI.

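### The SAP's MMRM example code enters country as both fixed and random, so the arm-level LSM confidence limits it requests rest on a variance the data cannot estimate

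*SAP*

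**What the plan says.** The text of SAP 6.9.2 gives the fixed effects of the MMRM as baseline value, severity group, biologic status, and then "country, treatment, study week, the treatment-by-week interaction, and the baseline-by-week interaction and allow for random subject effects". Protocol 16.6.2 places country in the same fixed-effect list ("country, treatment, study week, the treatment-by-week interaction"). Subject is the only random effect either text names.

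The example code in SAP 6.9.2 has `COUNTRY` in `CLASS` and `MODEL`, a `REPEATED` statement with unstructured covariance by subject, and then "RANDOM COUNTRY". It requests output through "LSMEANS TRTP*AVISITN / PDIFF CL", that is, arm-by-visit LSMs with confidence limits as well as the differences. The reported comparison is described in the text: "The LSM and 95% CI for the difference between groups will be estimated using the simple contrast at each time point".

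SAP 6.10 sends several exploratory endpoints to the method used for the "secondary efficacy continuous endpoint of percent change in EASI" (6.10.1, 6.10.4 to 6.10.7, 6.10.9 and 6.10.10).

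In SAP 6.9.1 a second block is introduced with "Below is an example of the SAS code for the Fisher's exact test". Its only table request is "table RESP / out=CNTS bin(cl=midp"), run separately by treatment group.

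**The concern.** The code does not fit the model that the text describes. Country has two levels, USA and Germany, and the fixed country term already absorbs any difference between them. A random country effect on top has nothing left to explain, so REML cannot estimate its variance. Any quantity that depends on that variance then depends on how the software treats a flat likelihood.

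At stake are the arm-level LSM intervals for percent change in EASI and for the exploratory endpoints analyzed the same way, if the example is copied into production. The independent reprogramming described in SAP Section 7 would not expose the error if both programmers work from the same example.

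In SAP 6.9.1 the matter is smaller. The block offered for Fisher's exact test cannot produce a between-arm p-value, so the named fallback test has no code.

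**Working it through.** SAP 6.9.2 states no numerical result to reproduce, so the check is algebra followed by a numerical confirmation.

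**Why the variance is not identifiable.** Let X be the fixed-effect design matrix and Z the two country indicator columns. Because X contains an intercept and country, Z = XA for some matrix A. REML uses only contrasts K′y with K′X = 0. Then K′Z = 0, and the country variance σ² drops out of the likelihood.

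**What it does to the estimates.** With V = V₀ + σ²ZZ′,

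Cov(β̂) = (X′V₀⁻¹X)⁻¹ + σ²AA′.

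- For the Week 14 between-arm difference, the contrast vector d has zeros on intercept and country. So d′A = 0, and the variance does not change.
- For an arm LSM, the vector l has 1 on the intercept and ½ on country, because `LSMEANS` weights the two countries equally. So l′A = (½, ½), and the added variance is σ²(¼ + ¼) = σ²/2.

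Hence SE² = SE₀² + σ²/2 for each arm.

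**Numerical confirmation.** The model was fitted by GLS/REML to a simulated trial.

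- From the documents: seven post-baseline visits, two countries split 55:15 as the sites are (SAP 3.1), about 40% IGA 4 (SAP 3.2), 65 per arm and 10% dropout (SAP 3.4).
- Assumed: SD of 40 points for percent change in EASI, decaying within-subject correlation, and 20% biologic-exposed.
- The within-subject covariance was held at its simulation value.

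Rank of X = 24 and rank of [X Z] = 24, so Z adds nothing.

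| Country variance | REML log-likelihood | Week 14 difference (SE) | Placebo LSM SE | Placebo 95% half-width | Active LSM SE |
|---|---|---|---|---|---|
| 0 | −3518.091806 | −6.6227 (7.23711) | 5.5569 | 10.89 | 5.9310 |
| 1 | −3518.091806 | −6.6227 (7.23711) | 5.6017 | 10.98 | 5.9730 |
| 25 | −3518.091806 | −6.6227 (7.23711) | 6.5863 | 12.91 | 6.9048 |
| 100 | −3518.091806 | −6.6227 (7.23711) | 8.9933 | 17.63 | 9.2291 |
| 400 | −3518.091806 | −6.6227 (7.23711) | 15.1947 | 29.78 | 15.3355 |

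Hand check of the last row: √(5.5569² + 400/2) = √(30.879 + 200) = 15.19. The placebo LSM itself stays at −40.39 throughout.

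A second simulated trial (130 subjects, 831 rows, 20% German) shows the same pattern at variances 0, 25, 100 and 400:

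- log-likelihood −3699.9304 each time;
- difference 2.294 (SE 6.597) each time;
- placebo LSM SE 5.89, 6.87, 9.20 and 15.32.

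Check: √(5.89² + 200) = 15.32.

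**The Fisher block in SAP 6.9.1.** Read against its label, the block tabulates response alone, by treatment group, and asks for mid-P binomial limits. It contains no treatment-by-response table and no Fisher or exact test request. Its own comment says that it computes an interval for each treatment, and calls that interval exact although the option requested is mid-P.

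**The case against.** The strongest reply is that nothing the text promises is shown to be wrong. The text governs, it lists country as fixed only, and the result it commits to is the between-arm LSM difference with its interval. That result does not move. The code is labelled an example, and the arm-level limits arise only from the `CL` option. If SAS returns zero for the country variance, those limits are correct too. All of this stands, and it sets the severity.

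Four stronger readings are tempting, and the documents do not support them.

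- **A reader might infer that the secondary test of percent change in EASI, or the gate in SAP 5.8, is compromised.** It is not: the difference and its standard error do not depend on the country variance.
- **A reader might infer that the arm intervals will be wrong, or as wide as the last table row.** That depends on what the software returns, which was not tested.
- **A reader might infer that the Mantel-Fleiss fallback in SAP 6.9.1 should be rewritten so that Fisher's test follows directly.** The wording is loose, but it can be read as a sequence, and the rewrite would delete a prespecified single-factor CMH step. At the planned 44% versus 15%, 0 of 6000 simulated trials reached the fallback. At lower rates assumed for IGA 0/1, for which the documents give none, the reading changed the verdict in at most 0.44% of trials.
- **A reader might infer that the mention of random subject effects is a further error.** No defect in it has been shown. The unstructured `REPEATED` covariance already carries within-subject correlation, and the phrase recurs in SAP 6.10.4, Protocol 16.6.2 and the protocol synopsis.

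On the Fisher block, it is fair to say that the text above it names the test plainly and leaves no analytical choice open. The block is still not the code it is said to be.

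**Conclusion.** The point holds as a code correction of low severity. The example code in SAP 6.9.2 contradicts its own text, and the random country variance it introduces cannot be estimated. If a nonzero value v is returned, each arm's LSM variance is too large by v/2. If zero is returned, there is no error.

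The flat likelihood, the unchanged difference and the v/2 rule are algebraic and need none of the simulation assumptions. The particular standard errors do depend on them, and the variances 1 to 400 are illustrations, not predictions. SAS was not run and the Kenward-Roger adjustment was not computed.

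The Fisher block is a minor labelling and coding gap in a fallback that is remote for the primary endpoint at the planned rates. No primary or gated secondary treatment comparison is affected by either item.

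**What to change.** **SAP 6.9.2.** Delete "RANDOM COUNTRY" from the example code. Keep `COUNTRY` in `MODEL` and `REPEATED` with `TYPE=UN`. Apply the same correction wherever SAP 6.10 reuses this model.

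**SAP 6.9.1.** Add a `TRTP*RESP` table with the `FISHER` option. Keep the existing block, relabelled as per-arm mid-P confidence intervals, since SAP 4.2.6 asks for an interval in each arm.

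Leave the Mantel-Fleiss fallback order and the random-subject wording as they are.

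The cost is one deleted code line, one added table request and one corrected label. Design, sample size, endpoints and the treatment contrast do not change.
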